### **12.1.6 Sensitivity Efficacy Analyses**

#### **12.1.6.1 Analyses Using Last Observation Carried Forward**

In the first set of sensitivity analyses, missing IGA values will be imputed using LOCF. Treatment success at Week 8 will be analyzed as it was in the primary analyses. Comparisons will be performed on imputed data using CMH tests stratified by analysis center.

#### **12.1.6.2 Repeated Measures Analysis on Observed Data**

As a second sensitivity analysis, treatment success at Week 8 will be analyzed with a repeated measures logistic regression model (generalized estimating equations), with treatment success as the dependent variable and treatment, analysis center and visit (Weeks 2, 4, 6 and 8) as independent factors.

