**Statistical methods:**

All subjects who are randomized and dispensed study drug will be included in the intent-to-treat (ITT) analysis set. All subjects in the ITT analysis set who complete the Week 8 visit without any major protocol violations will be included in the per protocol (PP) analysis set. All subjects who are randomized, receive at least 1 confirmed dose of study drug, and have at least 1 post-baseline assessment will be included in the safety analysis set.

The ITT analysis set will be considered primary for the evaluation of efficacy. The primary method of handling missing efficacy data will be the method of Markov Chain Monte Carlo (MCMC) multiple imputation; no imputations will be made for missing safety data.

*Efficacy:*Efficacy Endpoints

The efficacy endpoints are intended to compare once daily application of IDP-122 Lotion and vehicle. Specifically, the efficacy endpoints include:

- The percent of subjects with treatment success, defined as at least a 2 grade improvement from Baseline in the IGA score and an IGA score equating to “clear” or “almost clear” at Weeks 2, 4, 6, 8 and Week 12 (4-week follow-up), as summarized using descriptive statistics.
- The percent of subjects with at least a 2-grade improvement from Baseline in the score for each of the signs of psoriasis (erythema, plaque elevation, and scaling) at Weeks 2, 4, 6, 8 and Week 12 (4 week FU), as summarized using descriptive statistics for the target lesion treated with study drug.

Inferential Statistics**Primary Efficacy**

The primary efficacy endpoint will be the percent of subjects with treatment success, defined as at least a 2-grade improvement from Baseline in IGA score and an IGA score equating to “Clear” or “Almost Clear”. The primary efficacy endpoint will be used to compare once daily application of IDP-122 Lotion with its vehicle. The percent of subjects with treatment success at Week 8 will be analyzed using Cochran-Mantel-Haenszel (CMH) tests stratified by analysis center.

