## 12 Statistics

All statistical processing will be performed using SAS® unless otherwise stated. No interim analyses are planned. Except where noted, all statistical tests will be two-sided and will be performed at the 0.05 level of significance.

Descriptive statistics will be used to provide an overview of the efficacy and safety results. For categorical parameters, the number and percentage of subjects in each category will be presented. For continuous parameters, descriptive statistics will include n (number of subjects), mean, standard deviation, median, minimum, and maximum. Appropriate inferential statistics will be used for the primary and secondary efficacy variables.

The primary method of handling missing efficacy data will be the method of Markov Chain Monte Carlo (MCMC) multiple imputation. As a sensitivity analysis, the last observation carried forward method (LOCF) will be used (i.e., the last available on-therapy observation for a subject will be used to estimate subsequent missing data points). No imputations will be made for missing safety data.

A statistical analysis plan (SAP), describing all statistical analyses will be provided as a separate document. The SAP will be finalized prior to unblinding of the study treatments.

Amendment 1, Clinical Study Protocol, 14 October 2015

CONFIDENTIAL

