### **12.1.1 Primary Efficacy**

The primary efficacy endpoint will be used to compare once daily application of IDP-122 Lotion and vehicle.

The percent of subjects with treatment success at Week 8 will be analyzed using Cochran-Mantel-Haenszel (CMH) tests stratified by analysis center.

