### **12.1.2 Secondary Efficacy**

Similar to the primary endpoint analyses comparisons will be performed using CMH tests stratified by analysis center. The secondary efficacy endpoints will be:

- Percentage of subjects who show at least a 2 grade improvement and reach Clear to Almost Clear at Week 12 for IDP-122 Lotion verses IDP-122 Vehicle Lotion
- Percentage of subjects who show at least a 2 grade improvement and reach Clear to Almost Clear at Week 6 for IDP-122 Lotion verses IDP-122 Vehicle Lotion
- Percentage of subjects who show at least a 2 grade improvement and reach Clear to Almost Clear at Week 4 for IDP-122 Lotion verses IDP-122 Vehicle Lotion
- Percentage of subjects who show at least a 2 grade improvement and reach Clear to Almost Clear at Week 2 for IDP-122 Lotion verses IDP-122 Vehicle Lotion

Evaluation of the secondary efficacy variables will use a gated sequential procedure starting with the comparisons of the first bulleted item and proceeding onto the next item. The process will terminate if a nonstatistically significant value is observed.

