### 12.1.4 Pooling Analysis

The clinical study will be conducted under a common protocol for each investigational site with the intention of pooling the data for analysis. Every effort will be made to promote consistency in study execution at each study site. The study is intended to be conducted in a manner such that a minimum of 15 subjects will be randomized and included in the ITT population (i.e., approximately at least 10 subjects in the IDP-122 arm and at least 5 subjects in the Vehicle arm) for any investigator. In the event that there are too few subjects in a treatment arm for an investigator, then the investigator's data will be combined to achieve the desired sample size minimum per treatment arm. The combining of investigator data will be accomplished by taking the investigator with the smallest enrollment and combining it with the investigator with the largest, restricted to investigational sites that did not meet minimum enrollment. If there is a further need to combine data, then the data of the investigator with the second smallest enrollment will be combined with the investigator's data which had the second largest enrollment, and so on. This process will continue for all investigators who did not have a minimum of 15 subjects enrolled. The process of combining investigator data that have insufficient subjects per treatment arm will result in redefining the groups of investigators for the purposes of statistical analyses. These combined groups will be referred to as "analysis centers" in the statistical analyses.

Amendment 1, Clinical Study Protocol, 14 October 2015

CONFIDENTIAL

The consistency of treatment response will be investigated across the analysis centers subsequent to combining the data as described above. Statistical tests will be conducted to identify if there are extreme analysis centers that could affect the interpretation of common statistical and clinical conclusions. For the purpose of testing consistency of treatment response, the primary efficacy variable will be considered. The percent of subjects with treatment success at Week 8 will be analyzed with a logistic regression with factors of treatment group, analysis center, and the interaction term of treatment group by analysis center. Further examination will follow if the analysis results in a significant interaction term.

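### The repeated-measures sensitivity analysis is announced as a Week 8 analysis, but its listed main-effects model estimates one treatment odds ratio common to Weeks 2, 4, 6 and 8

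*Combined protocol and SAP*

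**What the plan says.** Section 12.1.6.2 states its target: "As a second sensitivity analysis, treatment success at Week 8 will be analyzed with a repeated measures logistic regression model". It then lists the model terms, "with treatment success as the dependent variable and treatment, analysis center and visit (Weeks 2, 4, 6 and 8) as independent factors". It names no interaction, no Week 8 contrast and no working correlation.

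The analysis being checked is the primary one in Section 12.1.1, which uses Week 8 alone: "The percent of subjects with treatment success at Week 8 will be analyzed using Cochran-Mantel-Haenszel (CMH) tests stratified by analysis center". Section 12.1.2 treats the other visits as separate secondary endpoints, for example "Percentage of subjects who show at least a 2 grade improvement and reach Clear to Almost Clear at Week 6".

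Where the protocol wants an interaction in a logistic model, it writes one out. Section 12.1.4 specifies "factors of treatment group, analysis center, and the interaction term of treatment group by analysis center", and later does the same for treatment by site. Section 12 adds: "A statistical analysis plan (SAP), describing all statistical analyses will be provided as a separate document". No text of that SAP is in the material available.

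**The concern.** A logistic model with treatment and visit as main effects lets the success rate rise or fall over visits but holds the treatment odds ratio equal at all of them. The reported coefficient is therefore a blend of Weeks 2, 4, 6 and 8. The protocol neither states nor tests that the odds ratio is constant.

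This GEE is the sensitivity analysis that uses observed data without imputation; the other one named in Section 12.1.6 is LOCF. A reader would take it as a check of the Week 8 result that does not depend on imputed values. If the effect changes over visits, it answers a different question. It would understate a Week 8 effect that builds late, and it could look favourable because of early visits when Week 8 shows nothing.

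**Working it through.** **Inputs from the protocol.** Week 8 success 33.3% v 9.7% (Table 5); 140 v 70 subjects, two-sided alpha 0.05 (Section 12.8.2).

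**The plan's own figure.** Exact enumeration of Fisher's test at 140 v 70 with these rates gives power 97.97%; the pooled normal formula gives 98.15%. Both agree with the stated power of more than 95%, which is not in dispute. The documents give no figure for the GEE.

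**Week 8 odds ratio.** (0.333/0.667) / (0.097/0.903) = 4.65.

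**What the listed model estimates.** Write logit(p) = a_k + b·treatment for visit k, leaving center aside. Under an independence working correlation and no missing data, the large-sample b solves two sets of conditions: at each visit the fitted successes over both arms equal the expected number, and over all four visits the fitted successes in the active arm equal the expected number. The second condition sums over visits, so only an overall treatment effect is matched, not the one at Week 8. The exchangeable values below were fitted to 300,000 simulated subjects at latent correlation 0.6, except the constant case, where the model is correct and the value is 4.65 under either structure.

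The rates before Week 8 are assumptions throughout. The last two rows also assume no effect at Week 8.

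| Assumed profile | Active %, Weeks 2, 4, 6, 8 | Vehicle %, Weeks 2, 4, 6, 8 | Odds ratio by visit | Common odds ratio, independence / exchangeable |
|---|---|---|---|---|
| Constant | 12.6, 19.7, 27.4, 33.3 | 3, 5, 7.5, 9.7 | 4.65 at each | 4.65 / 4.65 |
| Steady growth | 8, 16, 25, 33.3 | 4, 6.5, 8, 9.7 | 2.1, 2.7, 3.8, 4.65 | 3.55 / 3.95 |
| Late build-up | 5, 12, 22, 33.3 | 4, 8, 9, 9.7 | 1.3, 1.6, 2.9, 4.65 | 2.77 / 3.36 |
| Later still | 3, 7, 15, 33.3 | 3, 7, 9, 9.7 | 1.0, 1.0, 1.8, 4.65 | 2.32 / 2.99 |
| Early effect only | 10, 14, 13, 9.7 | 3, 5, 8, 9.7 | 3.6, 3.1, 1.7, 1.0 | 1.93 / 1.89 |
| Milder early effect | 8, 12, 12, 9.7 | 4, 6, 8, 9.7 | 2.1, 2.1, 1.6, 1.0 | 1.57 / 1.54 |

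**How often each test rejects.** Simulated trials of 140 v 70 in 14 centers of 10:5, with center in the model, latent correlation 0.6, center SD 0.3, robust standard errors and 0% or 10% monotone dropout; 1,500 trials per cell, Monte Carlo standard error at most 1.3 points. Centers with no success were left out and non-converged fits were excluded.

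| Profile | GEE as listed, independence | GEE as listed, exchangeable | Week 8 CMH |
|---|---|---|---|
| Constant | 99.9% | 99.9% | 98% |
| Steady growth | 97–99% | 98–99% | 97–99% |
| Late build-up | 87–89% | 95–97% | 98–99% |
| Later still | 65–71% | 83–89% | 98% |
| Early effect only | 45% | 45–46% | 5% |
| Milder early effect | 25–26% | 23–25% | 5% |

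**Joint behaviour when Week 8 shows no effect.** In 600 further trials for each of the last two profiles (independence, center omitted, no dropout), the GEE rejected in 39% and 21%, but the GEE and the primary test rejected together in only about 1–2%.

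**With the interaction and a Week 8 contrast.** Treatment and visit are then saturated, so in the calculation without center the Week 8 odds ratio is 4.65 in each of the first four rows, whatever the earlier visits show. In the simulations (exchangeable), rejection was within 1.1 points of the Week 8 CMH test in every cell.

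**The case against.** The strongest objection is that the SAP is a separate document, due before unblinding, and that interaction terms, contrasts and working correlations are normal SAP content. That stands as a limit. A reader might infer that the sponsor will in fact fit the wrong model, but the documents do not show that. They show that the protocol's own wording does not deliver the target it names. Terse drafting does not explain this away, because Section 12.1.4 spells out interactions when they are meant.

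A reader might take the 45% and 25% rejection rates as a false-positive risk for the trial. The documents do not support that. Those rates describe trials with no Week 8 effect, where the primary test rejects about 5% of the time, and a sensitivity analysis cannot rescue a failed primary. The early-only profiles also need active success rates to fall while treatment continues, and nothing in the documents suggests that.

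A reader might also infer a serious loss of power. That appears only under assumed late effects. It is negligible under constant or steadily growing effects, and under late build-up the exchangeable fit still rejects in 95–97%.

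Finally, a changing effect would not stay hidden. Success is reported "at Weeks 2, 4, 6, 8 and Week 12 (4-week follow-up), as summarized using descriptive statistics", and LOCF and per-protocol analyses exist. The CMH comparisons at Weeks 6, 4 and 2 would also help, although their gate may stop formal testing before they are reached.

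**Conclusion.** The point holds, at minor severity. As written, Section 12.1.6.2 announces a Week 8 analysis and lists a model for a common effect over Weeks 2 to 8. This is a mismatch between target and model, not merely a missing detail.

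It would be too strict to say that the two agree only if the odds ratio is constant, because unequal odds ratios could average to the Week 8 value by coincidence. The accurate statement is that the model does not target Week 8.

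Against a planned 4.65, the common odds ratio is about 3.6 under steady growth and about 2.3 to 2.8 under late build-up (independence), with smaller gaps under exchangeable. These sizes rest on assumed rates before Week 8, and the rejection rates also rest on assumed correlation, center variation and dropout. The documents give none of these. The consequence is confined to how this one sensitivity result is read.

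**What to change.** In Section 12.1.6.2, or in the SAP before unblinding:

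- Add the treatment-by-visit interaction and name the Week 8 treatment contrast (odds ratio, 95% CI, p-value) as the sensitivity result.
- State the working correlation, for example exchangeable with robust standard errors, falling back to independence if that fit does not converge.
- Pre-specify a sparse-data rule with two parts. A visit before Week 8 with no successes in an arm is left out, and Week 8 never is. An analysis center with no successes has no finite center estimate, so it is either left out or pooled by a stated rule. Leaving it out matches the CMH test, to which such a center contributes nothing.

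Alternatively, keep the model and relabel it as an average treatment effect over Weeks 2 to 8, which takes one sentence. If the SAP already specifies the contrast, only the protocol wording needs aligning.

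The costs are small. If the odds ratio really is constant, power falls from about 99.9% to about 98%. Under the assumed rates, an empty arm at a visit before Week 8 occurred in 7–17% of simulated trials, and the exchangeable fit with the interaction failed to converge in up to about 4%. At least one center with no successes occurred in about 2–8% of trials under the four planned-effect profiles, and in about 30% and 36% under the two with no Week 8 effect. That last problem affects the listed model too. The simulated performance of the revised model left such centers out and excluded non-converged fits, so it approximates rather than tests the full rule. The gain over an observed-case Week 8 test is modest; the main benefit is a result that means what its label says.

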### **12.1.7 Subgroup Analyses**

Subgroup analyses will be conducted for the ITT population for the following subgroups: Baseline IGA, sex, age, ethnicity, and race. Age will be dichotomized to less than the median age of subjects and greater than or equal to the median age of subjects. Subgroup analyses will be conducted on the primary efficacy endpoint and will contain only descriptive statistics.

## **12.2 Assessment of Safety**

### **12.2.1 Adverse Events**

The primary analysis of safety will be conducted at Week 8. There will be a tabulation, however, of the AE's that start in the period post the Week 8 to Week 12 visit. All AEs occurring during the study will be recorded and classified using terminology from the Medical Dictionary for Regulatory Activities (MedDRA). All reported treatment-emergent adverse events (TEAEs), defined as any AE with an onset on or after the date of first study drug application, will be summarized by treatment group and will provide the number of subjects reporting TEAEs, system organ class, preferred term, severity, and relationship to study drug. When summarizing TEAEs by severity or relationship to study drug, each subject will be counted only once within a system organ class or a preferred term using the event with the greatest severity or causality, respectively, within each category. All reported SAEs will be summarized by the number of subjects reporting the event, system organ class, preferred term, severity, and relationship to study drug.

All information pertaining to AEs noted during the study will be listed by treatment group and subject and will include a verbatim description of the event as reported by the investigator, as well as the preferred term, system organ class, start date, stop date (if stopped), seriousness, severity, action taken regarding the study drug, corrective treatment, outcome, and relationship to the study drug. In addition, a listing of subjects who prematurely discontinue from the study due to AEs will be provided as well as a listing of subjects who reported an SAE.

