## **11.1 Schedule of Evaluations and Procedures**

### **11.1.1 Screening Visit (Day -35 to Day -1)**

The following procedures will be conducted at this visit:

1. Obtain verbal and written informed consent from the subject prior to performing any study related procedures. Give a signed copy to the subject.
2. Review and explain the nature of the study. Provide a visit schedule with the length of each visit to ensure subject can meet the requirements and has adequate transportation.

3. Assign the subject a 6-digit subject number by accessing IRT, which will consist of the 3-digit site number (pre-assigned to your site) and the 3-digit chronological order screening number, assigned by the IRT system and starting with 001 (e.g., 101001, 101002, etc.; in this example site number is 101).
4. Record the subject's demographic information.
5. Record the subject's medical history.
6. Record all previous medications for psoriasis used during the past 6 months under Prior and Concomitant Medications or Therapies. Include all medications used in the past 30 days and any therapy that requires a washout prior to Baseline.
7. Record any prescription or over-the-counter therapies that are being used concomitantly under Prior and Concomitant Medications or Therapies. All medications taken within 30 days of the Screening visit should be recorded including any that may have ended prior to the Screening visit.
8. Record all previous cleansers, moisturizers, etc. in the past 30 days under Prior and Concomitant Medications or Therapies. Inform subjects that only Investigator-approved non-medicated cleansers, moisturizers, and sunscreens are allowed.
9. The investigator will assess the BSA affected by psoriasis and determine whether the locations of plaques are treatable with the study drug. The face, scalp, palms, soles, axillary areas, and other intertriginous areas will not count towards the total treatable BSA calculation.
10. The investigator/evaluator will conduct the IGA for the disease severity of the treatment areas. The face, scalp, palms, soles, axillary areas and other intertriginous areas will not be included in the severity score using the IGA scale. Every attempt should be made for the same sponsor-approved, qualified evaluator to perform the evaluations for the same subject.

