## **11.5 Adverse Events**

### **11.5.1 Definition of Adverse Event**

An AE is any untoward medical occurrence in a patient or clinical investigation subject administered a medicinal product and which does not necessarily have a causal relationship with the study drug. AEs include any unfavorable and unintended illness, sign, symptom, clinically significant laboratory test abnormality, or disease temporally associated with the use of a medicinal product that has appeared or worsened during the course of the clinical trial, regardless of causal relationship to the study drug(s) under study. The collection of nonserious AEs and serious adverse events (SAEs) should begin following the subject's completion of the consent process to participate in the study.

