### 11.5.2 Documenting Adverse Experiences

It is the responsibility of the investigator to document all AEs that occur during the course of the study. The AEs should be documented as a single medical diagnosis. When this is not possible, the AE should be documented in terms of signs and/or symptoms observed by the investigator or reported by the subject at each study visit.

All AEs occurring after the subject signs the informed consent through the last study visit must be reported, regardless of whether or not the AEs are considered drug-related. All AEs, whether in response to a query, observed by the study site personnel, or reported spontaneously by the subject, will be recorded.

At each visit during the study, the subject will be assessed for the occurrence of new and ongoing AEs. Cutaneous tolerability signs and symptoms that result in the subject's requiring a concomitant therapy or discontinuation from the study will be reported as an AE. The following data will be collected on all AEs and recorded on the appropriate eCRF:

- Event name (diagnosis preferred, if unknown, record the signs/symptoms)
- Onset date and end date
- Maximum intensity (severity)
- Seriousness
- Action taken regarding study drug
- Corrective treatment, if given
- Outcome

In addition, the investigator's assessment of causality will be recorded.

Vital sign abnormalities are to be recorded as AEs only if they are clinically significant (for example: are symptomatic, requiring corrective treatment, leading to discontinuation or fulfilling a seriousness criterion).

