### 11.5.4 Assessment of Severity

The severity assigned to an AE should be determined by the maximum severity of the AE. The categories described below should be used to estimate the severity of AEs:

- Mild: Transient or mild discomfort; no limitation in activity; no medical intervention/therapy required
- Moderate: Mild to moderate limitation in activity; some assistance may be needed; no or minimal medical intervention/therapy required
- Severe: Marked limitation in activity; some assistance usually required; medical intervention/therapy required; hospitalization or prolongation of current hospitalization possible; may be incapacitating or life threatening

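### Treatment-emergent events are defined by onset date alone, so a non-serious adverse event that starts before first application and worsens on study drug is left out of the TEAE tables as written

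*Combined protocol and SAP*

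**What the plan says.** The TEAE rule appears twice, in section 12.2.1 and in the Safety part of the synopsis, with the same wording: "defined as any AE with an onset on or after the date of first study drug application". Neither place mentions worsening.

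The definition of an adverse event in section 11.5.1 is wider. It covers an event "that has appeared or worsened during the course of the clinical trial". The same section says that collection "should begin following the subject's completion of the consent process", and section 11.5.2 repeats this: "All AEs occurring after the subject signs the informed consent through the last study visit must be reported". Section 11.1.1 places Screening between Day -35 and Day -1.

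On recording, section 11.5.2 lists "Onset date and end date" and one maximum intensity among the items for each event. Section 11.5.4 adds: "The severity assigned to an AE should be determined by the maximum severity of the AE". At Weeks 2, 4, 6, 8 and 12, the visit steps in sections 11.1.3 to 11.1.5 ask sites to record new events or changes to events already ongoing. No section says that a worsening receives its own record or its own date.

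**The concern.** The TEAE rule keeps only half of the protocol's own definition of an adverse event. An event that appears after dosing is counted. An event that was already present and was made worse after dosing is an adverse event under section 11.5.1 but is not treatment-emergent under section 12.2.1.

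Events that begin before dosing are a realistic possibility here. Subjects may spend up to 35 days between consent and Day 0, and section 11.1.1 allows a washout of earlier therapy in that time.

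The TEAE tables are the plan's main by-arm summary of non-serious adverse events by body system, severity and relationship. If aggravation by the drug cannot enter them, a difference between arms in that kind of event would show only in subject-level listings, which give no rates. If some sites record a worsening as a new event and others update the old record, the counts also depend partly on site habit.

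**Working it through.** The plan states no figure to reproduce. The check applies the written rule to each type of event, using the recording rules in sections 11.5.2 and 11.5.4.

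**Step 1. What the database would hold.** Take a hypothetical subject with a mild, non-serious event that starts on Day -10 and becomes severe on Day 12. The visit steps treat new events and changes to ongoing events as alternatives, so the natural entry is an update to the existing record. The onset stays at Day -10 and the maximum severity becomes severe. No field holds Day 12.

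**Step 2. Classification.** The written rule is: TEAE if onset date ≥ date of first application. The alternative is: TEAE if onset date ≥ date of first application, or severity increases on or after that date.

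| Event | Written rule | Onset or worsening |
|---|---|---|
| Starts before dosing, unchanged | No | No |
| Starts before dosing, worsens on drug | **No** | **Yes** |
| Starts on the Day 0 date | Yes | Yes |
| Starts later, on drug | Yes | Yes |

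Only the second row differs, and it is the event type that section 11.5.1 names when it includes worsening.

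**Step 3. Where the second-row event still appears.**

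- If serious: section 12.2.1 summarizes all reported SAEs by system organ class, preferred term, severity and relationship, with no TEAE restriction.
- If it is itching, dryness, burning/stinging, skin atrophy, striae, telangiectasia or folliculitis: section 12.2.2 tabulates these by arm and visit. It also tabulates any grade 3 itching, dryness or burning/stinging after the first application, whatever the onset date.
- If it is a laboratory change: section 12.2.3 provides shift tables.
- In all cases: the event is listed by subject. If it leads to discontinuation, the subject is also in the listing of discontinuations due to adverse events.

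What remains is a non-serious event that is neither one of the seven local reactions nor a laboratory change.

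**Step 4. Size.** The documents give neither the share of subjects with an event ongoing at Day 0 nor the share of those events that worsen. For illustration only, assume 5% to 15% for the first and 10% to 20% for the second:

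- Ongoing at Day 0: 210 × 0.05 = 10.5 to 210 × 0.15 = 31.5 subjects.
- Worsening afterwards: 10.5 × 0.10 = 1.05 to 31.5 × 0.20 = 6.3 events, both arms and all terms together.
- Active arm at 140/210: 1.05 × 140/210 = 0.7 to 6.3 × 140/210 = 4.2.

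These counts include events that Step 3 shows are tabulated elsewhere, so under the same assumptions the gap itself would be no larger and probably smaller. Both rates are assumptions, and the finding does not rest on them.

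**The case against.** The strongest reply is that the documents do not state the recording rule on which exclusion depends. Section 11.5.1 makes something that worsened during the trial an adverse event in itself, so a site could take the date of worsening as its onset, and the event would then be a TEAE. There is a second route. Table 1 does not mark adverse-event review at Screening, and the first Baseline step is to update medical history. A condition arising during washout might be entered as history, and its later worsening would be a new event with on-treatment onset. Both readings are possible. Neither is instructed, the history route sits badly with the requirement to report events from consent, and the wording of the visit steps points towards updating the old record. What stands is that the outcome may vary by site, and this is part of the point.

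The other replies limit the reach, and they stand. Skin problems on treated areas are partly covered already: a concurrent skin condition that could interfere with evaluation is an exclusion criterion, rechecked at Baseline, and a local reaction that leads to concomitant therapy, interruption or discontinuation must be reported as an adverse event. The documents do not say which onset date such a report takes when the reaction was already present at Baseline.

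A reader might infer three stronger things that the documents do not support:

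- That such an event vanishes from every table. It does not: the SAE summary, the local-reaction tables and the laboratory shift tables have no onset filter.
- That a large share of some rare severe or related category would be lost. Nothing in the documents, or in the illustration above, shows that the missing events would fall into one category.
- That counting every Day 0 event as treatment-emergent is a comparable error. It is an inclusive convention applied equally to both arms, and it needs no change.

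Section 12 also refers to a separate SAP. The text available contains no separate SAP, so whether one adds a worsening rule could not be checked.

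**Conclusion.** The point holds in a limited form. The TEAE definition in both places omits worsening. If it is applied together with the recording rules as written, it leaves a non-serious event that starts before dosing and worsens on drug out of the TEAE tables. Where sites enter the worsening as a new event, it is counted, so the tables may also be inconsistent between sites.

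The gap is confined to non-serious events outside the seven named local skin reactions and the laboratory data. Its size cannot be computed from the documents. The conclusion assumes that a worsening is normally entered as a change to the ongoing event, and that no separate SAP adds a worsening clause. It has no bearing on the efficacy analyses. It is worth correcting because the remedy is cheap and because a date of worsening that was never collected may not be recoverable at analysis.

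**What to change.** 1. In section 12.2.1 and in the synopsis, define a TEAE as an adverse event whose onset falls on or after the first-application date, or one with earlier onset that increases in severity on or after that date.
2. In section 11.5.2, tell sites how to record such a worsening: either as a new record with its own start date, or as a dated change in severity on the existing record. Choose one method for all sites. If the dated change is chosen, the data must let the analyst separate the maximum severity before first application from the maximum after it.

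The cost is one sentence in each of the two definitions and one eCRF completion instruction, plus a date field if the second method is chosen. No visit or efficacy analysis changes. The downside is that TEAE counts may rise slightly. A new record would not count a subject twice in the severity and relationship tables, because section 12.2.1 already counts each subject once per system organ class or preferred term there. The recording instruction should be in place before data collection, since it cannot be applied reliably afterwards.
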